### **3. GENERAL STATISTICAL METHODS**

#### **3.1. Sample Size Planned and Specified in the Protocol**

The previous pivotal, Phase 3, multicenter, randomized, open-label active- and double-blind placebo-controlled study of abaloparatide-SC (Study BA058-05-003) showed that the placebo-adjusted effect of abaloparatide-SC 80 µg on the percent change from baseline in lumbar spine BMD based on a Mixed-Effect Model Repeated Measures (MMRM) analysis was 9.096% (95% CI: 8.557%, 9.634%) at 12 months. According to FDA's *Guidance for Industry: Non-Inferiority Clinical Trials to Establish Effectiveness* (FDA, 2016), the lower bound of this confidence interval (CI) can be considered as the historical treatment effect of abaloparatide-SC versus placebo,  $M_1$  (=8.557%). Based on FDA's recommendation of a clinically meaningful difference of 2.0% between treatment groups, a non-inferiority (NI) margin,  $M_2$ , is selected at 2.0% to preserve approximately 77% of  $M_1$ , the historical treatment effect of abaloparatide-SC.

This preserved effect supports the superiority to placebo because the amount of preserved effect, 6.557% (=77%  $\times M_1$ ) is larger than the placebo-adjusted effect of alendronate 10 mg daily (5.4%; Fosamax® USPI) and of denosumab 60 mg once every 6 months (5.5%; Bolognese et al, 2013) on lumbar spine BMD at 12 months. Furthermore, the placebo-adjusted effect of teriparatide observed in the previous Phase 3 study (Study BA058-05-003) based on an MMRM analysis was 7.841% (95% CI: 7.384%, 8.297%). Thus, the proposed NI margin will preserve 89% (=6.557/7.384) of the effect of teriparatide, another market-approved anabolic agent.

Non-inferiority of abaloparatide-sMTS to abaloparatide-SC will be concluded if the lower bound of the two-sided 95% CI for the estimated treatment difference (abaloparatide-sMTS minus abaloparatide-SC) in the percent change from baseline in lumbar spine BMD at 12 months is above -2.0%, using an MMRM analysis.

A sample size of 426 subjects will provide at least 90% power to conclude the non-inferiority of abaloparatide-sMTS 300 µg to abaloparatide-SC 80 µg, assuming a true mean difference of 0% and a standard deviation of 6.35%. To ensure an analysis size of 426 subjects, an overall sample size of 474 subjects (237 subjects per group) will be randomized, anticipating that approximately 10% of treated subjects may not have both a baseline lumbar spine BMD measurement and at least one post-baseline lumbar spine BMD measurement.

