This preserved effect supports the superiority to placebo because the amount of preserved effect, 6.557% (=77% * M_1), is larger than the placebo-adjusted effect of alendronate 10 mg daily (5.4%; Fosamax® USPI) and of denosumab 60 mg once every 6 months (5.5%; Bolognese 2013) on lumbar spine BMD at 12 months. Furthermore, the placebo-adjusted effect of teriparatide observed in the previous Phase 3 study (Study BA058-05-003) based on an MMRM analysis was 7.841% (95% CI: 7.384%, 8.297%). Thus, the proposed non-inferiority margin leads to 89% (=6.557/7.384) of the effect of teriparatide, another approved anabolic agent.

Non-inferiority of abaloparatide-sMTS to abaloparatide-SC will be concluded if the lower bound of the 2-sided 95% CI for the estimated treatment difference (abaloparatide-sMTS minus abaloparatide-SC) in the percent change from baseline in lumbar spine BMD at 12 months is above -2.0%, using an MMRM analysis.

A sample size of 426 subjects will provide at least 90% power to conclude the non-inferiority of abaloparatide-sMTS 300 μ g to abaloparatide-SC 80 μ g, assuming a true mean difference of zero percent and a standard deviation of 6.35%. To ensure an analysis size of 426 subjects, an overall sample size of 474 subjects (237 subjects per group) will be randomized, anticipating that approximately 10% of treated subjects may not have both a baseline lumbar spine BMD measurement and at least 1 post-baseline lumbar spine BMD measurement.

Statistical Methods:

Analysis Populations:

The modified Intention-to-Treat (mITT) Population, defined as all randomized subjects who received at least 1 dose of study drug and had a baseline lumbar spine BMD measurement and at least 1 post-baseline lumbar spine BMD measurement, will be the primary population for the analyses of all efficacy endpoints. Supportive analyses of efficacy will be conducted using the Intention-to-Treat (ITT) Population, defined as all subjects randomized into the study, and the Per-Protocol (PP) Population, defined as all subjects in the mITT Population who did not have any critical protocol deviations (as defined in the Statistical Analysis Plan). The primary population for safety analyses will be the Safety Population, defined as all randomized subjects who received at least 1 dose of study drug.

Baseline Comparison:

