4.3.2. Handling of Subject Withdrawals or Terminations

If a subject is withdrawn or discontinued from the study, the reason for withdrawal from the study is to be recorded in the source documents and on the eCRF. All subjects withdrawn prior to completing 12 months of study drug treatment should be encouraged to complete study procedures scheduled for the Month 12/End of Treatment (EOT) visit as soon as possible, and to return in 1 month for a Follow-up visit (EOS Visit). All AEs should be followed as described in Section 7. Subjects who discontinue prematurely or are withdrawn from the study will not be replaced. For early terminations that occur on or after the day of study drug initiation, every effort should be made to document the subject's outcome, regardless of cause. Whenever a subject is discontinued prematurely, the Sponsor's Medical Monitor must be notified.

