8.5. Sample Size Calculation

The previous pivotal, Phase 3, multicenter, randomized, open-label active- and placebo-controlled study of abaloparatide-SC (Study BA058-05-003) showed that the placebo-adjusted effect of abaloparatide-SC 80 μg on the percent change from baseline in lumbar spine BMD based on a MMRM analysis was 9.096% (95% CI: 8.557%, 9.634%) at 12 months. According to Food and Drug Administration's (FDA) *Guidance for Industry: Non-Inferiority Clinical Trials to Establish Effectiveness* (2016), the lower bound of this CI can be considered as the historical treatment effect of abaloparatide-SC versus placebo, M₁ (=8.557%). Based on FDA's recommendation of a clinically meaningful difference of 2.0% between treatment groups, a non-

inferiority margin, M_2 , is selected at 2.0% to preserve approximately 77% of M_1 , the historical treatment effect of abaloparatide-SC.

This preserved effect supports the superiority to placebo because the amount of preserved effect, 6.557% (=77% * M₁), is larger than the placebo-adjusted effect of alendronate 10 mg daily (5.4%; Fosamax® USPI) and of denosumab 60 mg once every 6 months (5.5%; Bolognese 2013) on lumbar spine BMD at 12 months. Furthermore, the placebo-adjusted effect of teriparatide observed in the previous Phase 3 study (Study BA058-05-003) based on an MMRM analysis was 7.841% (95% CI: 7.384%, 8.297%). Thus, the proposed non-inferiority margin leads to 89% (=6.557/7.384) of the effect of teriparatide, another market-approved anabolic agent.

Non-inferiority of abaloparatide-sMTS to abaloparatide-SC will be concluded if the lower bound of the 2-sided 95% CI for the estimated treatment difference (abaloparatide-sMTS minus abaloparatide-SC) in the percent change from baseline in lumbar spine BMD at 12 months is above -2.0%, using an MMRM analysis.

A sample size of 426 subjects will provide at least 90% power to conclude the non-inferiority of abaloparatide-sMTS 300 μ g to abaloparatide-SC 80 μ g, assuming a true mean difference of zero percent and a standard deviation of 6.35%. To ensure an analysis size of 426 subjects, an overall sample size of 474 subjects (237 subjects per group) will be randomized, anticipating that approximately 10% of treated subjects may not have both a baseline lumbar spine BMD measurement and at least 1 post-baseline lumbar spine BMD measurement.

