## **2. SUBJECT ANALYSIS POPULATIONS**

### **2.1. Population Definitions**

Five subject populations will be considered in the statistical analyses of this study.

- Intention-to-Treat (ITT) population**

The ITT population consists of all subjects randomized into this study.

- Modified Intention-to-Treat (mITT) population**

The mITT population includes all randomized subjects who received at least one dose of study drug and had a baseline lumbar spine BMD measurement and at least one post-baseline lumbar spine BMD measurement.

- Safety population**

The Safety population consists of all randomized subjects who received at least one dose of study drug.

- Per-Protocol (PP) population**

The PP population consists of all mITT subjects who did not have any critical protocol deviations (described in [Section 2.2](#)).

- Antibody Population**

The Antibody population will include subjects in the Safety population who have at least one post-baseline anti-drug antibody assessment.

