**Table 3: Analysis Visit Windows for BMD, s-PINP and s-CTX Assessments**

Scheduled Visit / Month	Ideal Visit Day	Visit Window in Study Days	
		BMD	s-PINP and s-CTX
Visit 3 / Baseline	$\leq 1$	$\leq 1$	$\leq 1$
Visit 4 / Month 1	30		2-60
Visit 5 / Month 3	90	2 -120	61-120
Visit 6 / Month 6	180	121 - 300	121-300
Visit 8 / Month 12	360	$\geq 301$	$\geq 301$

It is possible that more than 1 assessment for a parameter may be obtained within the same analysis visit window. In such circumstances, the assessment with the date closest to the ideal visit day will be used. In the event that 2 assessments are equidistant to the ideal visit day, the later of the assessments will be used.

The analysis visit window convention will not be applied to the data listings. The data listings will display all data as collected with the corresponding nominal visit.

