##### **4.4.1. Primary Efficacy Endpoint**

###### **4.4.1.1. Primary Analysis**

The primary efficacy endpoint is the percent change from baseline in lumbar spine BMD at 12 months.

The primary hypothesis is that the effect of abaloparatide-sMTS 300 µg worn 5 minutes on the thigh on the percent change from baseline in lumbar spine BMD at 12 months is no worse than the effect of abaloparatide-SC 80 µg by a non-inferiority margin of 2.0%. Non-inferiority of

abaloparatide-sMTS to abaloparatide-SC will be concluded if the lower bound of the 2-sided 95% CI for the estimated treatment difference (abaloparatide-sMTS minus abaloparatide-SC) in the percent change from baseline in lumbar spine BMD at 12 months is above -2.0%, using an MMRM analysis.

The primary efficacy endpoint will be analyzed using an MMRM with fixed effects of treatment, DXA instrument manufacturer, visit, and treatment-by-visit interaction, and with baseline lumbar spine BMD as a covariate. Imputation for missing data is not necessary for the MMRM model because the model uses a restricted maximum likelihood (REML) based on the repeated-measures approach. An unstructured variance-covariance matrix will be used to model the within- and between-subject variabilities over the visits. The Kenward-Roger approximation will be used to estimate denominator degrees of freedom and to adjust standard errors ([Kenward and Roger, 1997](#)). Analyses will be implemented using the SAS PROC MIXED procedure. The least square (LS) means for the treatment groups and LS means and corresponding 95% CIs for the treatment differences (abaloparatide-sMTS minus abaloparatide-SC) at Month 12 will be derived from the MMRM model.

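### Does the 90% power claim for 426 subjects fail because the 10% allowance does not cover missing Month 12 scans?

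*SAP*

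**What the plan says.** Protocol section 8.5, the Protocol synopsis and SAP section 3.1 give the same calculation. The SAP states "A sample size of 426 subjects will provide at least 90% power to conclude the non-inferiority", "assuming a true mean difference of 0% and a standard deviation of 6.35" percent. The Protocol then says: "To ensure an analysis size of 426 subjects, an overall sample size of 474 subjects (237 subjects per group) will be randomized". The reason given is that "approximately 10% of treated subjects may not have both a baseline lumbar spine BMD measurement and at least 1 post-baseline lumbar spine BMD measurement".

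That allowance matches the scan part of the mITT definition in SAP section 2.1, which requires that a subject "had a baseline lumbar spine BMD measurement and at least one post-baseline lumbar spine BMD measurement". A Month 12 scan is not required.

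The decision rule in SAP section 4.4.1.1 is tied to Month 12. Non-inferiority is concluded if the lower 95% confidence bound for the difference "in the percent change from baseline in lumbar spine BMD at 12 months is above -2.0%, using an MMRM analysis". The model uses the observed visits without imputation.

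Two further provisions affect how many Month 12 values exist. Under Protocol section 4.3.2, subjects who stop early "should be encouraged to complete study procedures scheduled for the Month 12/End of Treatment (EOT) visit as soon as possible". SAP Table 3 ("Analysis Visit Windows for BMD, s-PINP and s-CTX Assessments") assigns BMD scans from study day 301 onward to Month 12, with no upper limit, and earlier post-baseline scans to Month 3 or Month 6.

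**The concern.** The allowance and the test refer to different things. The 10% is used up by subjects who fail the mITT scan criteria. A subject who has a Month 3 scan and then withdraws passes those criteria and counts among the 426, but informs the Month 12 comparison only through the correlation between visits. An early end-of-treatment scan before day 301 does not become a Month 12 value.

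The plan expects some Month 12 loss: SAP section 4.4.1.2 includes tipping-point, washout and LOCF analyses for it. Yet no Month 12 missing rate enters the power statement, and 426 has almost no reserve.

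Neither document says where 6.35% comes from. It could be a raw SD, an SD adjusted for baseline, or one derived from a model standard error. At stake is whether the only power figure in a trial with one primary test is overstated.

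**Working it through.** **Inputs from the documents.** Margin 2.0; true difference 0; SD 6.35; two-sided 95% interval (one-sided 0.025); 213 per arm analysed, 237 per arm randomized (SAP sections 3.1 and 4.4.1.1). Prior-study difference from placebo 9.096 (8.557 to 9.634) for abaloparatide-SC and 7.841 (7.384 to 8.297) for teriparatide (SAP section 3.1). Prior-study randomized arms: 824 abaloparatide-SC, 821 placebo, 818 teriparatide (Protocol section 1.1.2.2.1).

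**Assumptions, not in the documents.** m is the share of the 426 without a Month 12 scan. R² is the share of Month 12 variance explained by the earlier changes.

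**1. The plan's own figure.** SE = 6.35 × √(2/213) = 0.6153, and 2.0/0.6153 = 3.250.
- Normal formula: Φ(3.250 − 1.960) = 90.15%.
- Noncentral t with 424 degrees of freedom: 90.03%. With 212 per arm it is 89.89%.
- 426/0.9 = 473.3, so 474 in two equal arms.

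By the t calculation 213 is the smallest arm size that reaches 90%. This suggests that each of the 426 was treated as a full Month 12 observation, although no formula is stated.

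**2. If 6.35% is the residual Month 12 SD.** Effective n per arm = 213 / [1 + (1 − R²) m/(1 − m)]. For m = 10% and R² = 0 this is 213/1.111 = 191.7. Power by the normal formula:

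| m | R² = 0 | R² = 0.5 | R² = 0.7 |
|---|---|---|---|
| 5% | 88.6% | 89.4% | 89.7% |
| 10% | 86.9% | 88.6% | 89.2% |
| 15% | 85.0% | 87.6% | 88.6% |

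The t values are 0.1 to 0.2 points lower. The R² = 0 column is the worst case, because it gives Month 3 and Month 6 no predictive value for the same subject's Month 12 result.

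**3. If 6.35% is unadjusted for baseline.** The primary model adjusts for baseline BMD. If baseline explains an assumed 10% of variance, the residual SD is 6.35 × √0.9 = 6.02. With m = 10% and R² = 0, power is 90.0% (t).

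**4. The SD implied by the prior study.** SE = (9.634 − 8.557)/(2 × 1.96) = 0.2747. Dividing by √(1/824 + 1/821) = 0.04931 gives 5.57. This is an SD per randomized subject, taken from an MMRM standard error, so it already carries that study's Month 12 loss. The matching sample size here is the randomized 237 per arm, without a second deduction: power is 97.4% (t). The limitation is that 5.57 averages an active and a placebo arm, whereas this trial compares two active arms.

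**5. Whether 6.35% can be an abaloparatide-arm SD on the same basis.** Allow the arms different SDs and set abaloparatide-SC at 6.35.
- Placebo: √[821 × (0.2747² − 6.35²/824)] ≈ 4.67.
- Teriparatide: SE = (8.297 − 7.384)/(2 × 1.96) = 0.2329, so √[818 × (0.2329² − 4.67²/821)] ≈ 4.76.

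These values are consistent with both quoted intervals. That does not prove the source: there are three SDs and two intervals, so one SD has to be assumed. On this reading 6.35% already carries loss, and 237 per arm gives 92.8% (t).

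**The case for a change.** The strongest case for a change is that this is the trial's only power statement, that it appears in three places, and that one or two sentences would settle it. The endpoint is at Month 12, the plan prepares for missing Month 12 data elsewhere, and the MMRM does not recover everything: under the residual-SD reading, power is below 90% in every cell of the table above. The 10% could be redefined as loss of the Month 12 scan (474 × 0.9 = 426.6, which keeps 90%), or power could be given at a stated missing rate.

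The mismatch between allowance and endpoint stands, and so does the silence about the SD. The remedies add little. Redefining the 10% would credit the sponsor with a design assumption that the documents do not record, and would keep the 90% only by relabelling. Quoting a lower power needs a missing rate and a between-visit correlation that the documents do not give. SAP section 3.1 records a calculation already specified in the Protocol, and the SAP approvals date from September 2021, when the trial had long been running: the SAP separates subjects randomized before and after 01 March 2020. New wording there would not alter how many subjects were randomized.

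The absence of reserve is also weaker evidence than it looks. Any calculation that reports the smallest sufficient sample size falls below its target when one subject is removed.

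**Conclusion.** No change to the plan. The arithmetic is correct, and a shortfall in power is possible but not demonstrated. If 6.35% is the residual SD and an assumed 10% of mITT subjects lack a Month 12 scan, power is about 87% to 89%, roughly 1 to 3 points below the calculated 90.15%. If 6.35% is unadjusted and baseline BMD explains 10% of variance, power is 90.0% at the same loss. If the SD is per randomized subject and already carries loss, power is 92.8% at 6.35% or 97.4% at 5.57%. The documents do not allow a choice between these readings.

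What remains is missing description. It touches neither the number randomized nor the margin, model, population, interval or conclusion, and the precision achieved will be visible in the width of the confidence interval. The sponsor could usefully record the source and type of the 6.35% SD and the Month 12 loss assumed at design. The 10% should not be relabelled as a Month 12 allowance unless that was the design assumption.

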#### **3.2. General Methods**

Summary tables will be presented by treatment group (abaloparatide-sMTS and abaloparatide-SC) and overall, when appropriate. For categorical data, summary tabulations of the number and percentage of subjects within each category of the parameter will be presented. When tabulating categorical data, "missing" will be included as a category and the number of subjects with missing data will be presented. For continuous data, the number of subjects, mean, standard deviation (SD), median, minimum, interquartile range (Q1 and Q3), and maximum will be presented.

All data listings that contain an evaluation date will contain a relative study day. Screening, pretreatment, and on-treatment study days will be numbered relative to the day of the first dose of study drug which is designated as Day 1. Study days prior to the first dose of study drug will be calculated as: [date of assessment – date of first dose of study drug]. Study days on or after

the first dose of study drug will be calculated as: [date of assessment – date of first dose of study drug + 1].

Unless otherwise specified, all statistical tests will be two-sided with a significance level of 5%.

Where applicable, CIs about a parameter estimate will be presented using the same number of decimal places as the parameter estimate, and p-values will be rounded to 4 decimal places prior to assessment of statistical significance.

The anti-drug antibody assessment in the serum samples for immunogenicity testing will be analyzed and reported separately. All the planned efficacy and safety analyses related to immunogenicity results and antibody status will also be reported separately.

This study is being conducted during the COVID-19 pandemic. The COVID-19 outbreak emerged in December 2019 and quickly became a global pandemic as declared by the World Health Organization in early March 2020. At that time, a variety of mitigations to assure safety of participants and address operational issues were implemented by RADIUS. To investigate the effect of the COVID-19 pandemic on study conduct, additional analyses will be conducted as described in the efficacy and safety analysis sections.

### **3.3. Computing Environment**

All descriptive and statistical analyses will be performed using SAS statistical software Version 9.4 or later version. Medical history and AEs will be coded using the Medical Dictionary for Regulatory Activities (MedDRA), Version 24.0. Concomitant medications will be coded using the World Health Organization Drug Dictionary (WHO-DD) March 2018 B3.

### **3.4. Baseline Definitions**

The baseline value is defined as the last non-missing value obtained prior to the first dose of study drug, including the screening value, if necessary. If a randomized subject is not treated, the baseline value is defined as the last non-missing assessment.

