8.4. Description of Statistical Methods

8.4.1. General Approach

Analyses will be presented by treatment group (abaloparatide-SC and abaloparatide-sMTS) and overall, when appropriate. Baseline is defined as the last value obtained prior to the first dose of study drug.

For categorical data, summary tabulations of the number and percentage of subjects within each category of the parameter will be presented. For continuous data, the number of subjects, mean, median, standard deviation (SD), minimum, interquartile range (Q1 and Q3), and maximum will be presented.

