#### **4.4.1.2. Sensitivity Analysis**

The primary analysis using the MMRM model for the primary efficacy endpoint will be repeated using the ITT and PP populations to support the finding from the mITT population. Additional sensitivity analyses described below will also be performed in the mITT, ITT, and PP populations.

The primary analysis using MMRM model is based on the missing at random (MAR) assumption. To assess the impact of deviations from the MAR assumption for the primary analysis, a sensitivity analysis using the tipping-point approach will be conducted on the primary efficacy endpoint to assess the robustness of the primary analysis result.

The tipping point approach assesses how severe departures from MAR must be to overturn conclusions from the primary analysis. If implausible departures from MAR to change the results from being favorable to the experimental treatment to being unfavorable, the results will be said to be robust to the departure from MAR assumption. This provides additional confidence in the results obtained based on the MMRM model with the MAR assumption.

The tipping point analysis will only be performed if NI is concluded based on the primary analysis using MMRM.

Implementation of the tipping point analysis requires performing multiple imputation of missing lumbar spine BMD data under the missing not at random (MNAR) assumption with a sequence of shift parameters, which adjust the imputed values for the abaloparatide-sMTS treatment group.

Implementing the tipping point analysis include the following steps with the first three steps being the standard multiple imputation (MI) steps:

1. The missing data in both arms will be imputed 100 times to generate 100 complete data sets. The following process will be followed within Step 1:
  - a) A seed value of 940938 will be used in SAS PROC MI.

- b) The Markov Chain Monte Carlo (MCMC) method will be used to impute the intermediate missing values, so that the missing values follow a monotone pattern. One hundred data sets will be generated.
- c) For each of the 100 generated data sets, the monotone missing values will be imputed using the pattern-mixture model approach with a regression method. At this step, a shift parameter of zero will be applied. The SAS PROC MI methodology with the MNAR statement for imputation of monotone missing data patterns will be used in this step.

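### SAP 3.4 sets no date limit on baseline for randomised but untreated women, so a DXA taken after randomisation could become baseline in the supportive ITT analyses

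*SAP*

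**What the plan says.** SAP 3.4 gives two baseline rules. For dosed women: "The baseline value is defined as the last non-missing value obtained prior to the first dose of study drug", with the screening value allowed. For women randomised but never dosed: "If a randomized subject is not treated, the baseline value is defined as the last non-missing assessment". The protocol's rule (8.4.1) covers only the first group: "Baseline is defined as the last value obtained prior to the first dose of study drug".

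Untreated women belong to one efficacy population. SAP 2.1 states "The ITT population consists of all subjects randomized into this study", whereas "The mITT population includes all randomized subjects who received at least one dose of study drug" and also had a baseline and at least one later lumbar spine BMD. PP is a subset of mITT. Under SAP 4.4.1.2 the primary MMRM "will be repeated using the ITT and PP populations to support the finding from the mITT population".

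Time is anchored to dosing. SAP 3.2 says "on-treatment study days will be numbered relative to the day of the first dose of study drug", and SAP 3.12 likewise counts the ideal visit day from the first dose. Protocol 4.3.2 leaves a route to a later scan: "All subjects withdrawn prior to completing 12 months of study drug treatment should be encouraged to complete study procedures" of the Month 12/EOT visit, and Protocol 6.2.7.14 lists DXA among those procedures.

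**The concern.** The rule for dosed women has an upper time limit and the rule for undosed women has none. If an undosed woman has a screening DXA and a later one, the later one is literally the last non-missing value. Used as baseline, it leaves nothing after it to compare with, and her screening scan is ignored.

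This matters because of what the ITT repeat is for. The trial is open-label, so a woman can refuse treatment once she knows her assignment, and refusal could differ by arm; the documents give no evidence either way. The ITT analysis is the only one that can include these women, and as written the rule can remove the outcome information they have. SAP 4.3.2 refers to untreated subjects within ITT, so the plan's authors foresaw the case.

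**Working it through.** **1. The plan's own figures.** Inputs from SAP 3.1: margin 2.0, SD 6.35, true difference 0, two-sided 95% CI, power 90%.

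- Normal approximation: n per arm = 2 × (1.960 + 1.2816)² × 6.35² / 2.0² ≈ 211.8, so 212.
- Non-central t: 212 per arm gives 89.9% power and 213 gives 90.03%, so 426 in total.
- Allowance: 426 / 0.90 = 473.3, so 474 (237 per arm).

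The stated 426 and 474 reproduce, and this point does not alter them.

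**2. Who can make the ITT MMRM differ from the mITT MMRM?** The model needs a baseline covariate and at least one later value, and SAP 4.4.1.1 does not impute. A dosed woman with both lumbar spine values is already in mITT. The only extra contributors are therefore undosed women with a screening scan and a later scan, which is the group that the SAP 3.4 sentence mishandles.

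**3. The rule applied to the DXA schedule** (Screening and Months 3, 6 and 12; none on Day 1).

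- Screening scan only: baseline is the screening value, which is correct.
- Screening plus a later scan, with assumed values 0.800 and 0.792 g/cm²: the intended change is 100 × (0.792 − 0.800) / 0.800 = −1.0%. Under the literal rule 0.792 is baseline. The change is then undefined for the MMRM, or 100 × (0.792 − 0.792) / 0.792 = 0% if the record is reused at the nominal visit. LOCF also gives 0%, because its search range in SAP 4.4.1.2 includes baseline.
- The tipping-point and washout analyses are also planned in ITT. They would take the later scan as her baseline.

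**4. Visit placement.** With no first dose there is no study day, so Tables 3 and 4 cannot assign her scans to a visit. Capping baseline alone would not bring her into the windowed ITT analysis. The nominal-visit analysis (SAP 4.4 and 4.4.1.2) does not use study day and can still place them.

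**5. Scale.** The documents do not give k, the number of such women. Assume that all k are in the sMTS arm of 237, that the treated-arm mean is m = 9.096 (the placebo-adjusted abaloparatide-SC effect in SAP 3.1, used as a stand-in), and that their true change is c = 0% or −2%. Treat each later scan as a Month 12 value in a simple arm mean.

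- Mean with them kept: [(237 − k)m + kc] / 237. Mean with them dropped: m.
- Rise from dropping them: k(m − c) / 237. For k = 5 and c = 0: 5 × 9.096 / 237 = 0.192.
- Rise from coding them 0%: k(0 − c) / 237.

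| k | Dropped, c = 0% | Dropped, c = −2% | Coded 0%, c = −2% |
|---|---|---|---|
| 1 | 0.038 | 0.047 | 0.008 |
| 5 | 0.192 | 0.234 | 0.042 |
| 10 | 0.384 | 0.468 | 0.084 |

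Coding as 0% causes no shift when c = 0%. If 1–2% of those randomised were never dosed (an assumption), that is 0.01 × 474 = 4.7 to 0.02 × 474 = 9.5 women across both arms, and only those with a later scan count. The last row is therefore an extreme. Losses in the SC arm would move the difference the other way.

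**The case against.** The strongest reply is that the second sentence of SAP 3.4 exists only because an undosed woman has no first-dose date, and that its evident purpose is to let her screening value serve. A reader might infer that the SAP deliberately chooses follow-up scans as baseline. It does not say so. But it does not exclude them either, and a programmer who follows the words takes the latest scan. This is an unbounded definition, and the reply does not repair it.

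The reply on rarity stands. Randomisation and the observed first dose both fall on Day 1 at the site (Protocol 5.6, 6.2.7.1). Protocol 9.9 promises a completed eCRF only for dosed women, and the every-effort clause on outcomes in Protocol 4.3.2 applies from the day study drug is started. Most undosed women would probably have a screening DXA only.

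The reply on timing also stands. A reader might infer that a true 12-month outcome is deleted. Protocol 4.3.2 asks for the EOT procedures without delay after withdrawal, so the scan would usually come soon after Day 1. Counted from randomisation, days 2 to 120 fall in the Month 3 window of Table 3, where the scan informs Month 12 only through the correlation between visits. The shifts in the table above overstate that case. They fit better where an early scan is filed under the combined Month 12/EOT visit and analysed by nominal visit.

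Finally, it would be wrong to conclude that none of her scans can enter any analysis. The gap in study day affects the windowed analyses only.

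**Conclusion.** The point holds as a minor drafting defect. As written, SAP 3.4 can give the wrong baseline for a randomised, never-dosed woman who has a later recorded lumbar spine DXA. The result is a lost change in the ITT MMRM, or a spurious 0% under LOCF or reuse of the record at the nominal visit. The missing time anchor independently keeps her out of the windowed ITT analysis. Read literally, the windowed ITT MMRM then reproduces the mITT MMRM by construction and adds no independent support.

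The size rests on assumptions: the number of such women, their true change and their arm are not in the documents. Under the assumptions above, one woman dropped from sMTS shifts that arm's ITT mean by 0.04 to 0.05 points and five by 0.19 to 0.23, against a margin of 2.0. These are high-side figures for an early scan.

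A reader might infer that the non-inferiority conclusion is at risk. It is not: the decision rests on mITT, which excludes undosed women, so its result moves by 0.

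**What to change.** Replace the second sentence of SAP 3.4 with wording such as: *For a randomized subject who is never dosed, baseline is the last non-missing value on or before the date of randomization, and study day is counted from the date of randomization.* Cross-refer to it from SAP 3.2 and 3.12, so that Tables 3 and 4 apply to these women. Both halves are needed: the cap restores the correct baseline, and the anchor lets the windowed analysis place the later scan.

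The cost is one SAP sentence and a small programming change. It needs no new data and no change to the sample size or the primary analysis. Reporting the number of untreated women in each arm with a later lumbar spine DXA would show whether the point mattered in practice.
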